9.1. Design and Development

The DCC will be responsible for development of the electronic case report forms (eCRFs), development and validation of the clinical study database, ensuring data integrity, and

training clinical center staff on applicable data management procedures. A web-based distributed data entry model will be implemented. This system will be developed to ensure that guidelines and regulations surrounding the use of computerized systems used in clinical trials are upheld.

9.2. Data Collection Forms

The data collection process consists of direct data entry at the study clinical centers into the EDC system(s) provided by the DCC. A data collection worksheet will be provided to clinical centers for recording data in the event the EDC system is unavailable. Data entry of the eCRFs should be completed according to the instructions provided and project specific training. The investigator is responsible for maintaining accurate, complete and up-to-date records, and for ensuring the completion of the eCRFs for each research participant.

9.3. Data Acquisition and Entry

Data entry into eCRFs shall be performed by authorized individuals. Selected eCRFs may also require the investigator's written signature or electronic signature, as appropriate. Electronic CRFs will be monitored for completeness, accuracy, and attention to detail during the study.

9.4. Data Center Responsibilities

The DCC will 1) develop a data management plan and will conduct data management activities, 2) provide final eCRFs for the collection of all data required by the study, 3) develop data dictionaries for each eCRF that will comprehensively define each data element, 4) conduct ongoing data monitoring activities on study data, 5) monitor any preliminary analysis data clean-up activities, and 6) rigorously monitor final study data clean up.

9.5. Data Editing

Completed data will be entered into the DCC automated data acquisition and management system. If incomplete or inaccurate data are found, a data clarification request will be

generated and distributed to clinical centers for a response. Clinical centers will resolve data inconsistencies and errors and enter all corrections and changes into the DCC automated data acquisition and management system.

9.6. Training

The training plan for clinical center staff includes provisions for training on assessments, eCRF completion guidelines, data management procedures, and the use of computerized systems.

10. Data Analysis

10.1. Sample Size Determination and Randomization

We are planning to enroll approximately 58 subjects randomized in a 1:1 ratio to laparoscopic anti-reflux surgery or standard care. Patients will be allocated using a computer generated randomization scheme. Due to the unblinded nature of the study intervention, the randomization will not be stratified. If enough subjects randomized to surgery are unable to undergo surgery due to failure of insurance authorization or medical eligibility reasons, consideration will be given to rebalancing and/or adjusting randomization to insure sufficient subjects undergo surgery to meet the aims of the study.

In powering the study, we have considered the potential impact of PPI use for symptomatic GER (part of standard medical care) on the rate of FVC change in the no surgery group. Under the assumption that the use of PPIs will be partly effective, our statistical power will be reduced. Based on historical knowledge of change in FVC over time in patients with IPF a difference of 1.0 standard deviation over a one-year period would be approximately 0.25 liters. We believe that a treatment difference of that size would be both clinically meaningful and consistent with our preliminary data. We have conservatively estimated that 40% of individuals in the no surgery group will take PPIs on a regular basis for control of typical GER symptoms (i.e. heartburn and dyspepsia), and that PPIs are 50% as effective as surgery in reducing the rate of decline in FVC over time. With these adjustments, the expected effect size is reduced to 0.8 standard deviations. For that reason, this study is powered to detect an effect size of 0.8 standard deviations (or approximately 0.20 liters) in

the change in FVC between the two groups with a two-sided alpha of 0.05 and 80% power. The estimated number of subjects required for varying effect size and power are shown in Table 3. These calculations are based on the two-sample t-test with an increase in the sample size to allow for up to 10% withdrawal of consent.

Total subjects	Effect size	Two-sided alpha	Power
38	1.0	0.05	80%
52	1.0	0.05	90%
58	0.8	0.05	80%
76	0.8	0.05	90%
100	0.6	0.05	80%
134	0.6	0.05	90%

Table 3: Enrollment requirements for varying effect size and power

*Calculations allow for 10% withdrawal of consent.

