5.4 Study Design and Study Visits

Subjects who appear to meet entry criteria will review the informed consent (a written description of the purpose, procedures, and risks of the study) with the principal investigator (PI), co-investigator, or study coordinator, and all questions will be answered. The informed consent form will be signed by the subject at the beginning of the screening visit. No protocol-specific procedures will be performed until the subject has signed and dated an informed consent form. This includes the screening procedures.

The enrollment visit should occur within 90 days of the screening visit. However, it is preferred that the enrollment visit occur within 28 days of the screening visit to avoid repeating procedures.

All follow-up study visits will occur within 10 business days of their designation (e.g. week 12 will occur +/- 10 business days from the week 12 timepoint).

		Visit							
Study Procedure	Procedure details	Screen V1	Enroll V2	Surgery V2A	Wk 12 V3	Wk 24 V4	Wk 36 V5	Wk 48 V6	Wk 52
Medical history	 Complete medical history 	•							
Physical examination	Physical exam	•			•	•	•	•	
Documentation of GER	 Symptom questionnaire 	٠				•		•	Р
Assessment of esophageal motility and pH	> pH and manometry	•+				•&			H O N
Laparoscopic anti- reflux surgery *				•					Е
Bronchoscopy *				•				•^	V
Spirometry (Hand-held)									I S
Spirometry (Office based)		٠	•#		•!	•!	•!	•!	I T
DLCO			•		•!	•!		•!	
Arterial blood gas		•			•	•		•	
6 minute walk test		•	●#		•	•		•	
HRCT			•@					•	
Patient reported outcomes	 UCSD SOBQ Cough VAS SGRQ ICECAP EQ-5D 		•		•	•	•	•	
Blood collection			•		•	•	•	•	

Table 1. Table of Study Visits

* These procedures will be performed only in those subjects randomized to surgery.

+Does not need to be completed if done within 6 months of V2 at the study site in accordance with the study protocol.

@ Does not need to be completed if done within 3 months of V2 at the study site in accordance with the study protocol.

Only performed if V2 performed > 28 days after V1.

^ This is an optional procedure and will only be performed if the subject has consented for it.

! If a subject has undergone fundoplication surgery (regardless of treatment assignment) within 8 weeks of this visit date, the subject should not undergo this procedure.

& The pH and manometry should be done a minimum of 12 weeks after surgery, and only in those subjects randomized to surgery.

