At screening, all potential subjects will undergo a complete medical history, physical examination and testing (spirometry (performed pre-bronchodilator), arterial blood gas, GER symptom questionnaire, and 6 minute walk testing) with assessment of eligibility according to the inclusion and exclusion criteria. All potential subjects who meet entry criteria based on these assessments will undergo 24-hour pH testing and esophageal manometry, unless these procedures have been performed within 6 months of the enrollment visit (Visit 2) at the study site in accordance with the study protocol.

Subjects meeting eligibility criteria will return for an enrollment visit within 90 days (but preferably within 28 days), and will complete baseline evaluations as outlined in this protocol, including:

- Physical examination
- Diffusing capacity of the lung for carbon monoxide (DLCO)
- High-resolution computed tomography (HRCT) (unless performed in the past 3 months according to study protocol and available for review and databasing)
- Patient reported outcome questionnaires
 - UCSD Shortness of Breath Questionnaire (UCSD SOBQ)
 - St. George's Respiratory Questionnaire (SGRQ)
 - Cough visual analog scale (VAS)
 - ICECAP-O
 - EuroQOL EQ-5D
- Blood collection (5 tsp) for measurement of biomarkers

If the enrollment visit occurs within 28 days of screening, the screening values for spirometry and the 6 minute walk test (6MWT) will be recorded as the baseline values. If the subject is unable to return for enrollment until more than 28 days from screening, the spirometry and 6MWT procedures will need to be repeated, and those measurements recorded as the baseline values.

Enrolled subjects will be randomized to either receive anti-reflux surgery or standard medical care.

Subjects randomized to anti-reflux surgery will undergo additional evaluations as directed by the surgical team (these may include but are not limited to esophagram, endoscopy, and echocardiography) and will have pre-surgical evaluation by anesthesiology. These subjects

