will undergo preapproval for billing the laparoscopic anti-reflux surgery and related activities and tests to the subject's insurance (all other study procedures will be paid for by the study). In the unlikely event that a randomized subject is denied authorization, the subject will not have surgery but will be followed on an intention to treat basis. All subjects in the surgical arm will receive a bronchoscopy at the time of surgery. Bronchoscopy is a separate procedure from the surgical intervention. Bronchoscopy will be performed according to standardized protocol and samples (BAL and endobronchial brushings) will be collected. These patients will then undergo surgery according to study protocol (see section 8). They will have a post-operative visit with the surgeon at approximately 2 weeks to ensure appropriate recovery.

Subjects randomized to no surgery will be followed clinically. If there is evidence of significant disease progression (defined by a relative decline in FVC of \geq 10% over 24 weeks or longer), these patients will be allowed to undergo laparoscopic anti-reflux surgery as part of the clinical trial. These patients will otherwise complete the study visits as scheduled.

All subjects in the study will be provided with a home spirometer and instructed to perform spirometry daily throughout the course of the clinical trial. Subjects who are randomized to surgery will be instructed to halt daily spirometry from the date of their surgery until they return to the site for the week 12 visit.

Subjects will be blinded to the results of the home spirometry measurements. Subjects will be instructed to bring home spirometers to each study visit so that data can be downloaded and sent to the DCC for databasing. Subjects will have the option after study completion to keep the home spirometer for personal use.

Safety assessments: Subjects will be contacted by telephone for safety assessments in months where no study visit occurs (months 1, 2, 4, 5, 7, 8, 10, 11) and at week 52. The calls should visits will occur within 10 business days of their designation (e.g. month 1 will occur +/- 10 business days from the month 1 timepoint). One month is defined as 28 days. These phone calls will involve confirming the subject's vital status and asking questions about serious adverse events or adverse events related to the surgical procedure, for subjects randomized to surgery.

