The DCC will submit a detailed report of pre-specified AEs of interest and all SAEs monthly to NHLBI and DSMB chair. In addition, each SAE will be reported to NHLBI and DSMB chair by DCC within one business day after receiving the report. The DSMB Chair will review the information presented and determine if any additional information is needed, and/or a DSMB teleconference should be held. Guidelines for the DSMB procedures will be detailed in the DSMB charter.

8. Surgical Intervention

Subjects randomized to laparoscopic anti-reflux surgery will undergo preoperative evaluation by the surgical team after randomization. This will include a standard preoperative surgical assessment, anesthesia clearance, and other testing as medically indicated. During surgery, standard American Society of Anesthesiologists protocols will be used to monitor patients under general anesthesia. All subjects will be mechanically ventilated using the minimal tidal volumes and supplemental oxygen required to maintain adequate gas exchange. All subjects who undergo laparoscopic anti-reflux surgery will have a post-operative visit to insure appropriate recovery. There will be no scheduled study procedures during this visit.

Laparoscopic anti-reflux surgery generally involves the following steps. Individual patient issues may require modifications depending on the surgeon's intraoperative assessment. All efforts will be made to adhere exactly to the same surgical procedure, but if needed, the surgical team can deviate from the standardized protocol to ensure the safety of the patient and to achieve maximum beneficial results. Completion or modification of each stage will be documented in the clinical research form.

Step 1: Division of gastrohepatic ligament; identification of right crus of the diaphragm and posterior vagus nerve.

Step 2: Division of peritoneum and phreno-esophageal membrane above esophagus; identification of the left crus of diaphragm and anterior vagus nerve.

Step 3: Division of short gastric vessels.

Step 4: Creation of a window between gastric fundus, esophagus, and diaphragmatic crura.

Step 5: Placement of Penrose drain around the esophagus.

Step 6: Closure of crura.

Step 7: Insertion of the bougie into esophagus and through esophageal junction.

Step 8: Wrapping of gastric fundus around lower esophagus.

Step 9: Final inspection, removal of instruments and trocars from the abdomen, and closure of the port sites.

9. Data Management

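### Should payer approval and surgical and anaesthesia clearance be completed before randomisation rather than after it?

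*Combined protocol and SAP*

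**What the plan says.** Section 5.4 randomises patients at the enrolment visit. The steps that finally settle whether a patient can be operated come afterwards, in one arm. Section 5.4: "Subjects randomized to anti-reflux surgery will undergo additional evaluations as directed by the surgical team", with an anaesthesiology evaluation, and these patients "will undergo preapproval for billing the laparoscopic anti-reflux surgery". Section 8: "Subjects randomized to laparoscopic anti-reflux surgery will undergo preoperative evaluation by the surgical team after randomization". It then adds: "This will include a standard preoperative surgical assessment, anesthesia clearance, and other testing as medically indicated".

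Before randomisation, section 5.1 requires manometry acceptable for the full operation. In section 5.3, exclusion 8 covers safety of the full operation and exclusion 12 covers the likelihood of payer approval; both rest on the investigators' judgement. Section 5.4 calls denial of authorisation unlikely and keeps a denied patient in follow-up by intention to treat.

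Section 10.1 foresees some failures. It begins "If enough subjects randomized to surgery are unable to undergo surgery due to failure of insurance authorization or medical eligibility reasons" and says that rebalancing or adjusting the randomisation will then be considered. It gives no trigger or ratio.

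On timing, section 5.4 states: "The enrollment visit should occur within 90 days of the screening visit" (28 days preferred). Table 1 places surgery (V2A) between enrolment and week 12, without a stated interval. Two of its footnotes depend on the date of surgery. One cancels spirometry and DLCO: "If a subject has undergone fundoplication surgery (regardless of treatment assignment) within 8 weeks of this visit date". The other reads: "The pH and manometry should be done a minimum of 12 weeks after surgery"; that test is scheduled at week 24.

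**The concern.** Eligibility appears to be completed after allocation, and in one arm only, of an unblinded trial. A patient found unfit or refused by a payer remains in the surgery arm without the operation and pulls the two arms together. The effect size in section 10.1 is lowered from 1.0 to 0.8 SD for PPI use in controls only, and the 10% inflation is for withdrawal of consent only, so 58 subjects leave nothing in reserve for this.

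Waiting for approval and clearance may also delay surgery, while the 48-week clock runs from baseline. If surgery works by slowing the rate of decline, the weeks before it contribute no difference. Under the Table 1 footnotes, the week-12 spirometry is lost if surgery comes after about week 4 (12 − 8), and the week-24 pH test fits only if surgery is done by about week 12 (24 − 12).

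The contingency named in section 10.1 would yield more operated patients but would not restore the intention-to-treat comparison. Doing the checks inside the existing 90-day window looks like a neater answer, with the sample size and the 1:1 ratio unchanged.

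**Working it through.** **Inputs (section 10.1).** 58 subjects at 1:1, so 29 per arm; two-sided alpha 0.05; 80% power; SD of change about 0.25 L; 40% of controls on PPIs that are 50% as effective as surgery; 10% withdrawal; two-sample t-test. Power below is from the noncentral t distribution.

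**The plan's own figure.** Effect = 1.0 − 0.40 × 0.50 = 0.8 SD, or 0.8 × 0.25 = 0.20 L. The t-test needs 26 per arm (power 80.7%); 52 / 0.90 = 57.8, rounded up to 58. The other five rows of Table 3 reproduce in the same way. With no withdrawal (29 per arm), power is 84.9%.

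**Unoperated patients.** The documents give no rate, so k is assumed. If k of 29 are unoperated and behave like controls, d = 0.8 × (1 − k/29).

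| k | d (SD) | Power, 26 per arm | Power, 29 per arm |
|---|---|---|---|
| 0 | 0.800 | 80.7% | 84.9% |
| 1 | 0.772 | 78.0% | 82.4% |
| 2 | 0.745 | 75.0% | 79.6% |
| 3 | 0.717 | 71.8% | 76.6% |

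Each unoperated patient costs about 3 percentage points. If those patients are the ones who withdraw, they fall within the 10% allowance and power stays at 80.7%, although losing less fit patients from one arm would not be neutral.

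**Delay.** Assume further that the effect accrues linearly from surgery at a mean of w weeks: d = 0.8 × (48 − w)/48.

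| w (weeks) | d (SD) | Power, 26 per arm | Power, 29 per arm |
|---|---|---|---|
| 4 | 0.733 | 73.7% | 78.4% |
| 8 | 0.667 | 65.4% | 70.4% |
| 12 | 0.600 | 56.4% | 61.2% |

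**Are the longer delays plausible?** Table 1 places V2A before week 12. Section 5.4 stops home spirometry from surgery until the week-12 visit, which presumes that surgery has already taken place. A mean of 12 weeks would put the average operation at that visit, and a mean of 8 weeks would leave most week-12 spirometry cancelled. The 8-week footnote is not in itself a sign of expected delay: it applies whatever the assigned arm, so it also covers controls operated later after progression. A mean of a few weeks is the most that the schedule supports.

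**Changing the ratio.** With 3 unoperated and 90% retained, 29:29 gives 71.9%. At 32:26, d = 0.8 × 29/32 = 0.725 and power is 72.4%. At a fixed total the ratio does little for the primary comparison.

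**What reordering would need.** About 29 future controls would have a surgical and anaesthesia assessment and a payer request that they do not have now. If a fraction f fails, 58/(1 − f) otherwise eligible patients must be worked up: 62, 65, 69 or 73 for f = 5, 10, 15 or 20% (assumed). Any gap above 28 days requires repeat spirometry and 6-minute walk tests. Against this, the gain at 26 per arm is 80.7 − 78.0 = 2.7 points if one patient would otherwise go unoperated, and 80.7 − 71.8 = 8.9 points if three would.

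**The case for a change.** The strongest case for a change is that section 10.1 itself expects failures on insurance and medical grounds, that the sample size ignores them, and that small numbers matter: one unoperated patient together with a mean delay of 4 weeks gives d = 0.8 × 28/29 × 44/48 = 0.708 and power of 70.7% (75.5% with no withdrawal). Rebalancing does not repair this. The 90-day window already exists, and repeat spirometry after 28 days would keep the baseline current.

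The order of steps, the missing allowance and the weakness of rebalancing all stand. The rest is weaker:

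- The large losses come from delay, and reordering sets no limit on time to surgery. The documents do not say how much of any delay is due to approval or clearance and how much to scheduling.
- Linear accrual from baseline is an assumption. Section 10.1 uses rate-of-decline language for the PPI adjustment, but what is powered is a 0.20 L difference in change. The surgical series in section 4.2, with FVC measured on average 105 days before and 115 days after surgery, showed a rise of 0.08 L.
- The documents give no durations for payer decisions or clearance. Fit within 90 days, after pH testing and manometry, is unproven, and a payer may decline to rule on an operation not yet assigned. If only clinical clearance could be moved, the insurance cause would remain and the rebalancing sentence would still be needed.
- Replacing investigator judgement with actual clearance and authorisation would make eligibility stricter in practice.
- Refusal after allocation would remain possible.

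**Conclusion.** No change to the plan follows. Table 3 and the 58 subjects are correct for the stated assumptions, and no figure in the plan is missed. The cost of the present order is a possible loss of about 3 percentage points of power for each unoperated surgery patient, from 80.7% with 26 evaluable per arm to 71.8% at three, on the assumption that such patients behave like controls. A mean delay of 4 weeks would by itself lower power to 73.7% under linear accrual; longer means do not sit well with the visit schedule.

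How many patients would fail is unknown. Exclusions 8 and 12 and manometry screen both arms beforehand, and denial is described as unlikely. Intention-to-treat follow-up protects the validity of the comparison if failures occur, and section 10.1 commits only to considering an adjustment. Reordering would spend study resources on about 29 controls and on every screen failure, with unproven feasibility and no cap on time to surgery, for a benefit that cannot be sized from the documents. That is a trade-off on which a sponsor may reasonably keep the present order. A documented rate of refusals or failed clearances of 10% or more, about 3 of 29, would be a reason to look again.

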5.1. Inclusion Criteria

Only subjects with confirmed IPF, abnormal GER on 24-hour pH monitoring (as defined by a DeMeester score of > 14.7) and esophageal manometry that is acceptable for full laparoscopic anti-reflux surgery will be eligible for this study. Subjects must be able to provide informed consent and be willing to undergo laparoscopic anti-reflux surgery.

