5.3. Exclusion Criteria

- 1. FVC < 50% predicted
- 2. FEV1/FVC ratio < 0.65
- 3. Resting room air PaO2 < 60mm Hg
- 4. Unable to walk 50 meters on 6 minute walk test
- 5. Recent acute respiratory illness in last 12 weeks
- 6. Participated in an interventional clinical trial for an IPF therapy in the last 28 days (subjects may be screened, but cannot be enrolled until 28 days after trial participation) [Note: open-label extensions or expanded access programs (EAPs) for pirfenidone or nintedanib are not considered interventional clinical trials and are not exclusionary.]
- 7. Listed for lung transplantation at screening
- 8. Unable to safely undergo full (complete) laparoscopic gastric anti-reflux surgery (i.e. not a partial fundoplication), in the judgment of the investigators
- 9. History of esophageal / bariatric / gastric surgery
- 10. History of cancer (other than non-melanoma skin cancer) in the last 3 years
- 11. Pregnant at the time of screening or enrollment
- 12. Unlikely to obtain pre-authorized approval from a third party payer for laparoscopic anti-reflux surgery and related costs in the opinion of the investigators.
- 13. Life expectancy < 48 weeks due to another illness
- 14. BMI > 35
- 15. Known severe pulmonary hypertension (mean pressure > 35 mm Hg on RHC; RVSP > 50 mm Hg on ECHO)

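### Does the expected 0.8 SD overstate power because it allows nothing for surgery-arm subjects who are never operated on?

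*Combined protocol and SAP*

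**What the plan says.** Section 10.1 of the combined protocol and SAP starts from a difference of 1.0 SD, about 0.25 L. It assumes that 40% of the no-surgery group take PPIs regularly and that PPIs are half as effective as surgery, and concludes: "With these adjustments, the expected effect size is reduced to 0.8 standard deviations". It then states that "this study is powered to detect an effect size of 0.8 standard deviations (or approximately 0.20 liters"). The calculation is a two-sample t-test with an "increase in the sample size to allow for up to 10% withdrawal of consent". Table 3 gives 58 subjects for 0.8 SD at 80% power.

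The same section has a contingency. "If enough subjects randomized to surgery are unable to undergo surgery due to failure of insurance authorization or medical eligibility reasons", then "consideration will be given to rebalancing and/or adjusting randomization to insure sufficient subjects undergo surgery to meet the aims of the study". It gives no expected rate, no trigger and no power figure for this.

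Other sections bear on how often it could happen. Section 5.1 admits only subjects with "esophageal manometry that is acceptable for full laparoscopic anti-reflux surgery will be eligible for this study", who must also "be willing to undergo laparoscopic anti-reflux surgery". Section 5.3 excludes anyone "Unable to safely undergo full (complete) laparoscopic gastric anti-reflux surgery" (exclusion 8) and anyone whose insurer is thought unlikely to approve the operation (exclusion 12). Section 5.4 describes refusal of authorisation after randomisation as unlikely and keeps such subjects in follow-up under intention to treat. Section 8 places the surgical and anaesthetic work-up after randomisation.

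**The concern.** The plan models dilution in one arm and is silent about dilution in the other. PPI use raises the control mean and is deducted. Unoperated subjects pull the surgery mean towards control and are not deducted, although Section 10.1 names two routes by which they arise. The 10% withdrawal allowance does not obviously cover them: a subject who stays in follow-up without surgery still contributes FVC values and still dilutes the contrast.

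Because 0.8 SD is called the expected effect, a reader may take 80% as the realistic chance of success. If non-receipt were appreciable, the true figure would be lower, and the trial could miss an effect that it was thought able to detect. Rebalancing the allocation looks like a weak remedy for this, because it does not remove the dilution.

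**Working it through.** **Inputs.** From Section 10.1: 58 subjects at 1:1, two-sided alpha 0.05, 80% power, 1.0 SD = 0.25 L, PPI use 40%, PPI efficacy 50% of surgery, withdrawal up to 10%. The share q of retained surgery-arm subjects who are unoperated is not in the documents, so every value of q below is an assumption.

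**The plan's own figures.** The PPI deduction is 1.0 − 0.40 × 0.50 = 0.80 SD, and 0.80 × 0.25 = 0.20 L. With the noncentral t, the smallest number per arm reaching 80% for 0.8 SD is 26 (power 80.7%; 25 gives 79.1%). Then 52/0.9 = 57.8, so 58. The other five rows of Table 3 need 17, 23, 34, 45 and 60 per arm. Doubled and divided by 0.9 these give 37.8, 51.1, 75.6, 100 and 133.3, against the printed 38, 52, 76, 100 and 134. The table is right. If nobody withdraws, 29 per arm gives 84.9%.

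**Adding non-receipt.** Measure benefit in SD units. Operated subjects gain 1.0. Controls gain 0.40 × 0.50 = 0.2. Suppose unoperated surgery-arm subjects use PPIs as controls do and also gain 0.2. The difference is

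(1 − q)(1.0) + q(0.2) − 0.2 = 0.8(1 − q).

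| q among retained | Effect (SD) | Power, 26 per arm | Power, 29 per arm |
|---|---|---|---|
| 0 | 0.80 | 80.7% | 84.9% |
| 5% | 0.76 | 76.6% | 81.2% |
| 10% | 0.72 | 72.1% | 76.9% |
| 15% | 0.68 | 67.2% | 72.1% |

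Power equals 80% at q = 0.96%, 2.9%, 4.7% and 6.4% with 26, 27, 28 and 29 per arm. If unoperated subjects took no PPI at all, the effect would be 0.8 − q, and 10% would give 69.7% at 26 per arm. If all took PPIs it would be 0.8 − 0.5q, and 10% would give 75.6%.

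**Whole subjects.** With 26 evaluable per arm, one retained unoperated subject is q = 1/26 and gives 77.6%; three give q = 3/26 and 70.6%. If those same subjects are among the three per arm who withdraw, power stays at 80.7%. With no withdrawal, one of 29 gives 82.4% and two give 79.6%.

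**Scale.** A PPI share of 45% instead of 40% gives 1.0 − 0.45 × 0.50 = 0.775 SD and 78.2% at 26 per arm. One unoperated subject therefore costs about as much as a five-point error in the PPI guess.

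**Changing the allocation.** Suppose 4 of 29 are unoperated: power is 68.4% at 26 per arm. Shifting four places to surgery within 58 (30 against 22 evaluable) gives 67.4% to 69.0%, taking q as 4/29 or 4/33. Adding four to surgery (30 against 26) gives 71.5% to 73.1%.

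**Drift after a ratio change.** Suppose 30 subjects enter at 15:15 and then 28 at 18:10. The late share is 18/33 = 54.5% in surgery and 10/25 = 40.0% in control, a gap of 14.5 points. An assumed shift of 0.05 to 0.10 L between periods would bias the difference by about 0.007 to 0.015 L. The standard error of the difference is about 0.25 × √(2/26) = 0.069 L.

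**The case for a change.** The best case for a change is that the plan names this dilution itself, quantifies the parallel one in controls, and could mend the omission with a few sentences. It is also true that screening does not settle the matter: the work-up comes after randomisation, and the description of refusal as unlikely covers insurance only. Section 5.4 states intention to treat for subjects refused authorisation but does not say the same of those found medically unfit. All of this stands as description.

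It does not show that a stated figure is wrong. The tolerance of about 1.0% is mainly the 0.7 points of slack left by rounding up to 26 per arm, a quarter of one patient. Any trial sized just to reach 80% is equally intolerant of whatever it did not model. That figure also requires withdrawal to reach its ceiling and non-receipt to be wholly separate from it. A statement that 80% holds only if virtually everyone is operated on would be inaccurate, since three unoperated subjects who withdraw leave 80.7%.

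The 10% and 15% rows and the 4-of-29 scenario have no basis in the documents. On rebalancing, Section 10.1 gives the total as approximate and does not rule out adding subjects. A period covariate would answer a ratio change that may never happen and a bias well inside the standard error. As for reading a null result, Section 10.2 provides treatment contrasts with confidence intervals. Those, with the observed count of unoperated subjects, say more than planning power does. Analysts would keep medically unfit subjects in their randomised arm, in line with Section 5.4.

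**Conclusion.** No change is called for. Fifty-eight subjects do give 80% power for 0.8 SD, and Table 3 reproduces. What remains is an unstated assumption: calling 0.8 SD expected presumes negligible non-receipt among retained surgery-arm subjects. Under the assumption that unoperated subjects fare like controls, 5% non-receipt would leave about 77% to 81% power and 10% about 72% to 77%, depending on withdrawal. The documents give no rate, but screening for manometry, willingness, surgical safety and payer approval suggests a low one. One such subject leaves 77.6% at full withdrawal or 82.4% at none, and costs nothing if already among the withdrawals. Writing the assumption down would be harmless, but it would not alter the sample size, the test, the primary analysis or any figure shown to be wrong. The conclusion would need another look if a non-receipt rate of around 10% or more were documented as expected.
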